6.6.3. Criteria and Procedures for Dose Interruptions and Adjustments of Study Drug

Safety concerns should be discussed with the sponsor immediately upon occurrence or awareness to determine if the participant should continue or discontinue study treatment.

There are no dose modifications in this study. In some circumstances, it may be necessary to temporarily interrupt treatment with INCB054707 as a result of AEs or laboratory abnormalities that have an unclear relationship to the study drug (see [Table 8](#)). Except in cases of emergency, it is recommended that any laboratory findings be confirmed and that the investigator consult with the sponsor medical monitor (or other representative of the sponsor) before temporarily interrupting study drug. Participants who experience a recurrence of the AEs or laboratory abnormalities upon restarting the study drug may have the study drug permanently discontinued.

Table 8: Guidelines for Interrupting, Restarting, and Discontinuing Study Drug

ADVERSE EVENT	ACTION TAKEN
Chemistry	
AST and/or ALT $> 3.0 \times \text{ULN}$	
Step 1: Interrupt study drug administration up to 2 weeks (14 days) until the toxicity has resolved to $\leq 3.0 \times \text{ULN}$.
 
Step 2: Restart study drug, and monitor as described specifically in Section 9.3.

AST and/or ALT $> 5.0 \times \text{ULN}$	Discontinue study drug administration, and monitor as described specifically in Section 9.3.
Hematology	
Platelet counts 50 to $< 100 \times 10^9/\text{L}$ or $\geq 50\%$ decrease from baseline	
Step 1: Interrupt study drug administration up to 2 weeks (14 days) until the toxicity has resolved to $\geq 100 \times 10^9/\text{L}$.
 
Step 2: Restart study drug, and monitor as described in Section 9.3.

ANC 0.5 to $< 1.0 \times 10^9/\text{L}$	
Step 1: Interrupt study drug administration up to 2 weeks (14 days) until the toxicity has resolved to $\geq 1 \times 10^9/\text{L}$ or the baseline value.
 
Step 2: Restart study drug, and monitor as described specifically in Section 9.3.

Hemoglobin 8 to $< 10 \text{ g/dL}$ or $> 2 \text{ g/dL}$ decrease from baseline	
Step 1: Interrupt study drug administration up to 2 weeks (14 days) until the toxicity has resolved $\geq 10 \text{ g/dL}$ or $\leq 2 \text{ g/dL}$ decrease from baseline.
 
Step 2: Restart study drug, and monitor as described specifically in Section 9.3.

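### Protocol Table 8, platelet row: a count that interrupts study drug only through the 50% fall from baseline already meets the stated restart number (baselines of 200 ×10⁹/L or more)

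*Protocol*

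**What the plan says.** The platelet interruption row of Table 8 in Protocol Section 6.6.3 has two alternative triggers, one absolute and one relative: "Platelet counts 50 to $< 100 \times 10^9/\text{L}$ or $\geq 50\%$ decrease from baseline". Step 1 allows an interruption of up to 14 days, "until the toxicity has resolved to $\geq 100 \times 10^9/\text{L" (that is, 100 ×10⁹/L or more). Step 2 is to restart. No restart term refers to baseline. A separate row discontinues study drug at a platelet count below 50.

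The hemoglobin row is the only other interruption row with an absolute and a baseline-relative trigger: "Hemoglobin 8 to $< 10 \text{ g/dL}$ or $> 2 \text{ g/dL}$ decrease from baseline". Its restart text has two limbs: "until the toxicity has resolved $\geq 10 \text{ g/dL}$ or $\leq 2 \text{ g/dL}$ decrease from baseline".

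Safeguards elsewhere:

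- Section 6.6.3: "Safety concerns should be discussed with the sponsor immediately upon occurrence or awareness". Except in emergencies, "it is recommended that any laboratory findings be confirmed and that the investigator consult with the sponsor medical monitor" before interrupting. Recurrence after restart may lead to permanent discontinuation.
- Section 8.6: the investigator must inform and consult the sponsor about any hematological abnormality. A potentially clinically significant abnormality at Week 2, 4 or 6 requires a repeat visit the following week. For interruption and restart, this section points to Section 6.5.

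Exclusion criterion 8 in Section 5.2 removes participants with a screening platelet count below 150 ×10⁹/L and sets no upper limit.

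**The concern.** A restart condition should be false while the reason for stopping is still true. The platelet restart number is the complement of the absolute trigger but says nothing about the relative one. If the relative trigger can hold at counts of 100 or more, the table tells the site to interrupt and, on the same result, that the restart number is satisfied.

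Platelets matter in this safety study. Sections 8.3.5.1 and 8.6 single them out for repeat testing, and Section 9.5 makes platelet decreases an adverse event of special interest. Taken literally, the row cancels its own relative trigger. Sites and the medical monitor would have to settle each such case themselves, and two sites could handle the same count differently.

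**Working it through.** There is no sample size or power figure to reproduce; this is a consistency check on one table row.

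**Inputs (×10⁹/L).** From Table 8, with baseline B and current count P:

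- absolute trigger: 50 ≤ P < 100
- relative trigger: (B − P)/B ≥ 0.50, that is, P ≤ B/2
- restart: P ≥ 100

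**Step 1: when do a trigger and restart hold together?** The absolute trigger and restart cannot both hold. The relative trigger and restart both hold when 100 ≤ P ≤ B/2, which requires B ≥ 200.

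**Step 2: put in baselines.** The values of B are illustrative.

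| Baseline B | B/2 | Counts meeting trigger and restart | Fall at a count of 100, (B − 100)/B |
|---|---|---|---|
| 150 | 75 | none | 33.3% |
| 199 | 99.5 | none | 49.7% |
| 200 | 100 | 100 only | 50.0% |
| 250 | 125 | 100 to 125 | 60.0% |
| 300 | 150 | 100 to 150 | 66.7% |
| 400 | 200 | 100 to 200 | 75.0% |

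**Step 3: where does the relative trigger do any work?** If B < 200, then B/2 < 100. Any count low enough to meet the relative trigger is then already in the absolute band, or below 50 and in the discontinuation row. The relative trigger acts alone only when P ≥ 100, and every such count meets the restart number. The overlap therefore covers all interruptions that rest on the relative trigger alone. Example: B = 300 and P = 140 is a fall of 160/300 = 53.3%. Interruption is triggered, and 140 ≥ 100.

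**Step 4: interruptions that began in the absolute band.** At B = 300, a participant interrupted below 100 who recovers to 105 meets the restart number. The fall is still 195/300 = 65.0%, so the relative trigger is still met at restart.

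**Step 5: the other interruption rows with numeric limits.**

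- AST/ALT: the trigger is above 3.0 × ULN and restart is "until the toxicity has resolved to $\leq 3.0 \times \text{ULN". These are complementary.
- ANC: the trigger is 0.5 to below 1.0 and restart is "until the toxicity has resolved to $\geq 1 \times 10^9/\text{L}$ or the baseline value". There is no overlap if baseline is at least 1.5. That figure is a screening exclusion, whereas SAP Section 4.1.3 takes baseline as the last value before first dose, and Day 1 hematology is also drawn. With a Day 1 value of 0.9, a later 0.9 would meet both cells, so the row is complementary only conditionally.
- Hemoglobin: if each restart limb is paired with its own trigger, there is no overlap. If *or* is read literally, there is. A fall from 14 to 11.5 g/dL is a decrease of 2.5 (trigger) and is at least 10 (restart). A fall from 11 to 9.5 g/dL is in the 8 to below 10 band (trigger) and is a decrease of 1.5 (restart). The table does not say which reading is meant.

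**The case against.** The strongest reply is that the word *resolved*, together with the consultation requirements, carries the rule. A low count that has not recovered has not resolved. Table 8 is headed as guidelines, Section 8.6 makes sponsor consultation mandatory, a repeat visit can be required, recurrence may end treatment, and a count below 50 ends it. Every overlap count is at least 100, well above the limit of 75 below which Table 7 defines a platelet dose-limiting toxicity. No analysis error is shown.

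Much of this stands. The consequence is limited, and case-by-case discussion with the sponsor is part of the written process. But Section 6.6.3 places its confirmation and consultation advice before interrupting, the recurrence sentence applies after restart, and Section 8.6 gives no restart criterion. The only end point attached to *resolved* is 100 or more. If the verb also means that the 50% fall must clear, the table does not say so.

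Some stronger readings are not supported:

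- **That the protocol is silent on when such an interruption ends.** It is not: it states 100 or more. The fault is that this number contradicts the relative trigger.
- **That a count worsening from 140 to 105 at a baseline of 300 would count as resolved.** That takes the number without the verb. Step 4 of the working, where the count rises to 105, does not have this weakness.
- **That every other row is clean and only the platelet row is at fault.** AST/ALT and ANC have single triggers and are not like comparisons, ANC is clean only under a baseline assumption, and hemoglobin is ambiguous.
- **That dose escalation or the SAP's interruption summaries are compromised.** Escalation uses the dose-limiting toxicity definition, and an effect on the summaries is possible but not shown.

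**Conclusion.** The point holds as an internal contradiction in one table row. For baselines of 200 ×10⁹/L or more, counts from 100 to half of baseline satisfy the relative platelet trigger and the restart number together, and this covers every interruption that rests on the relative trigger alone. For baselines below 200 the relative trigger adds nothing to the absolute one. This follows from the two cells themselves and does not depend on the screening limit.

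The documents give neither a baseline platelet distribution nor an expected size of fall, so the number of participants affected cannot be stated. The safeguards reduce the consequence without removing the contradiction. It is worth correcting because the parameter is one of special safety interest and the correction is small. The hemoglobin wording is an ambiguity only, and the Section 8.6 pointer is an editorial slip; neither is needed for the platelet conclusion.

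**What to change.** The sponsor's medical team should reconcile the trigger and restart cells of the Table 8 platelet row, so that the text says when an interruption for a fall of 50% or more from baseline may end. No threshold or form of rule is proposed here.

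Two minor, separate clarifications can go in the same amendment:

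- State how the two hemoglobin restart limbs pair with the two hemoglobin triggers.
- Change the Section 8.6 reference for interruption and restart from Section 6.5, which covers dose-limiting toxicity and cohort review and has no restart rule, to Section 6.6.3.

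The cost is a small protocol amendment with IRB/IEC approval before implementation (Section 11.1) and a memo to sites. The sample size, the escalation rule and the planned analyses do not change.

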
 Platelet count $< 50 \times 10^9/\text{L}$ ANC $< 0.5 \times 10^9/\text{L}$ ANC $< 1.0 \times 10^9/\text{L}$ with an oral temperature of at least 38.5°C OR with \geq Grade 3 infection Hemoglobin $< 8 \text{ g/dL}$ 	Discontinue study drug administration, and monitor as described specifically in Section 9.3.
Other toxicities	
Any Grade 1 or Grade 2 toxicity	Continue study drug and treat the toxicity; monitor as described specifically in Section 9.3.
Any Grade 3 toxicity except those defined in Table 7 (exception for any \geq Grade 3 nonhematologic toxicity)	
Step 1: Interrupt study drug up to 2 weeks (14 days), until toxicity resolves to \leq Grade 1.
 
Step 2: Restart study drug and monitor as described specifically in Section 9.3.

Any other Grade 4 toxicity	Discontinue study drug administration and follow-up as described in specifically Section 8.8.

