8.6. Unscheduled Visits

Unscheduled visits may occur at any time at the investigator's discretion, and appropriate clinical and laboratory tests may be performed, as clinically indicated.

If there is a potential clinically significant abnormality in hematology or chemistry assessments (particularly in platelet count) at Weeks 2, 4 or 6, an unscheduled visit the following week (Weeks 3, 5, 7) to repeat hematology assessments is required (see Section 8.3.5.1). See Section 6.5 for the instruction of dose interruption and restart. The investigator must inform and consult sponsor with any hematological abnormality.

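### Table 8 joins the two hemoglobin restart limits with 'or', so when both hold triggers fired its literal text permits restart with one still met

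*Protocol*

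**What the plan says.** The hemoglobin row of Table 8 (Protocol Section 6.6.3) starts a hold for "Hemoglobin 8 to $< 10 \text{ g/dL}$ or $> 2 \text{ g/dL}$ decrease from baseline". Drug is interrupted for up to 14 days, "until the toxicity has resolved $\geq 10 \text{ g/dL}$ or $\leq 2 \text{ g/dL}$ decrease from baseline", and Step 2 is to restart. Hemoglobin below 8 g/dL means permanent discontinuation, so the hold zone starts at 8.

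Four other provisions bear on how the row is read:

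- The table is titled "Guidelines for Interrupting, Restarting, and Discontinuing Study Drug".
- Section 6.6.3 opens by sending safety concerns to the sponsor "to determine if the participant should continue or discontinue study treatment". It recommends contact with the medical monitor before an interruption.
- Section 8.6 is firmer: "The investigator must inform and consult sponsor with any hematological abnormality".
- Two neighboring rows are built differently. The platelet row also has two triggers, "Platelet counts 50 to $< 100 \times 10^9/\text{L}$ or $\geq 50\%$ decrease from baseline", but a single restart limit of 100 × 10⁹/L. The ANC row holds "until the toxicity has resolved to $\geq 1 \times 10^9/\text{L}$ or the baseline value", where *or* offers a true alternative.

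**The concern.** If a hold starts when A or B is true, neither is true only when not-A and not-B both hold. The hemoglobin row mirrors its triggers limit for limit but keeps *or*. When both triggers fired, the row does not say that both must clear. A site that follows the words can therefore resume dosing while one of the abnormalities that caused the hold persists. The trigger cell would then call for a new hold, so the row tells the site both to restart and to stop.

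Safety and tolerability is the primary objective, and Section 10.1 names hemoglobin among the adverse events of interest behind the cohort size. With about 9 active participants per dose level, sites that read the cell differently would re-dose at different hemoglobin levels.

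**Working it through.** The plan gives no calculated figure for this row, so the check is of its logic.

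**Inputs from the documents.** Trigger A: 8 ≤ Hb < 10. Trigger B: baseline − Hb > 2. Restart limits: Hb ≥ 10; baseline − Hb ≤ 2. Discontinue: Hb < 8. Exclusion criterion 8d (Section 5.2) excludes Hb < 10 at screening.

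**Assumption.** Baselines (b) run from 10.0 to 18.0 g/dL in 0.1 steps, with Hb from 8.0 up to baseline. Only the floor of 10 comes from the documents.

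**Counting hold states (pairs of baseline and Hb with at least one trigger on).**

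- Baselines 10.0 to 12.0: 21 baselines × 20 Hb values = 420.
- Baselines 12.1 to 18.0: 21 + 22 + … + 80 = 3030.
- Total: 420 + 3030 = 3450.

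Both triggers on:

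- Baselines below 12: 1 + 2 + … + 19 = 190.
- Baseline 12.0: 20.
- Baselines above 12: 60 × 20 = 1200.
- Total: 190 + 20 + 1200 = 1410.

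One trigger only: 3450 − 1410 = 2040.

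**One trigger fired.** If only A fired, the fall is already ≤ 2. If only B fired, Hb is already ≥ 10. The literal rule is therefore satisfied at the start of all 2040 such holds, and the hold would end as it began. That cannot be intended, so each limit must answer its own trigger here.

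**Both triggers fired.** Neither limit is met at the start of any of the 1410 holds. As Hb rises, the literal rule is first met at min(10, b − 2). Both triggers are off only at max(10, b − 2). The gap is |(b − 2) − 10| = |b − 12|.

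| Baseline | Hb where both fire | Literal restart | Both off | Gap |
|---|---|---|---|---|
| 10.5 | 8.0–8.4 | 8.5 | 10.0 | 1.5 |
| 11.0 | 8.0–8.9 | 9.0 | 10.0 | 1.0 |
| 11.5 | 8.0–9.4 | 9.5 | 10.0 | 0.5 |
| 12.0 | 8.0–9.9 | 10.0 | 10.0 | 0 |
| 12.5 | 8.0–9.9 | 10.0 (fall 2.5) | 10.5 | 0.5 |
| 13.0 | 8.0–9.9 | 10.0 (fall 3.0) | 11.0 | 1.0 |
| 14.0 | 8.0–9.9 | 10.0 (fall 4.0) | 12.0 | 2.0 |

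At a baseline of 12 or more, every Hb from 8.0 to 9.9 fires both triggers. At a baseline of exactly 10.0 they cannot both fire at Hb 8 or above.

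**Paired rule against AND.** Requiring every trigger that fired to clear gives the same restart level as requiring both limits, in all 3450 states.

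**Search for another restart level.** Hemoglobin also appears in criterion 8d (screening), Table 7 (Grade 4 anemia as a dose-limiting toxicity), the Table 8 discontinuation row and Section 10.1. None says when drug may resume after a hemoglobin hold.

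**The case against.** The case on the other side has four parts.

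1. The row speaks of the toxicity having resolved, and its left cell defines that toxicity by either trigger. While one is on, the toxicity is arguably unresolved. The either-limit reading also defeats itself in every single-trigger hold. This stands as support for the paired reading, on which the gap is 0. It does not supply the missing words for the both-trigger case, and *or* in the ANC row is a true alternative.
2. Restart need not be the exact opposite of the trigger. On the platelet row, a participant with baseline 300 held at 90 restarts at 100 with a fall of 200/300 = 67% still present. An absolute floor overriding a relative fall is thus a pattern in the table, and 10 g/dL is the level accepted at screening. This makes the examples above baseline 12 less clear-cut. It does not explain restart below 10 g/dL, which the literal text permits for baselines between 10 and 12.
3. Sponsor consultation on any hematological abnormality is required, Table 8 is guidance, and recurrence after restart may lead to discontinuation. These lower the risk, but the sponsor would be advising from the same cell.
4. Reach is narrow: a fall that is both below 10 and more than 2 g/dL, then partial recovery within 14 days, among about 27 active participants. This stands.

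Two stronger inferences are tempting. A reader might conclude that a participant with baseline 14 held at 11 solely for the fall may restart at once. The row's mirrored order and the absurd result of that reading count against it. A reader might also conclude that participants will be re-dosed unsafely or that the trial's results will be affected. The documents give no frequency and require consultation, and the point touches no sample-size or analysis figure.

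**Conclusion.** The concern holds as a wording gap in one safety rule. Read literally, when both triggers fired, Table 8 permits restart with one still met. This is clearest for baselines under 12 g/dL, where restart can fall inside the hold band, and arguable for baselines above 12. The gap is |baseline − 12| g/dL on the either-limit reading and zero on the paired reading. These are hemoglobin levels at assumed baselines, not patient frequencies, and the documents do not allow a count of affected participants. Practical risk is low because the paired reading is natural and consultation is required. Severity is low.

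**What to change.** Replace the restart condition with: until hemoglobin is ≥ 10 g/dL AND the decrease from baseline is ≤ 2 g/dL. Notify sites.

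Do not add an exception for baselines below 10 to the restart text alone. Criterion 8d applies at screening, so a Day 1 baseline of, say, 9.8 is possible, and AND would then require 10.0, above that participant's own baseline. But allowing restart at 9.8 while the 8 to below 10 trigger stays unchanged would recreate the conflict between restarting and holding. If an exception is wanted, write it into that trigger as well, so that trigger and restart agree.

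The cost is one table cell in a protocol amendment and a site notice. Compared with the literal reading, some holds last longer (at baseline 14, until 12.0 rather than 10.0) and some may reach the 14-day limit. Compared with the paired reading, no restart level changes for baselines of 10 g/dL or more.

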6.7. Concomitant Medications and Procedures

All concomitant medications and treatments (including over-the-counter or prescription medicines, vitamins, vaccines, and/or herbal supplements) must be recorded in the eCRF. Any prior medication received up to 28 days before the first dose of study treatment and 30 days after the last dose of study treatment will be recorded in the eCRF. A detailed history of prior medications use related to HS in the year before screening will be also be collected, as well as response to each treatment and reason for discontinuation.

Any addition, deletion, or change in the dose of these medications will also be recorded. Concomitant treatments/procedures that are required to manage a participant's medical condition during the study will also be recorded in the eCRF. The medical monitor should be contacted if there are any questions regarding concomitant or prior therapy.

6.7.1. Permitted Medications and Procedures

6.7.1.1. Antibiotic Therapy

After Week 4, if a participant experiences signs or symptoms indicative of an infection at an HS site (eg, fever and local/regional lymphadenopathy), the following antibiotic therapy may be initiated without interruption of study drug administration:

- Amoxicillin 500 mg/clavulanic acid 125 mg, 2 tablets, 3 times daily for 3 days

In participants for whom amoxicillin is contraindicated, the investigators should consult with the sponsor or designee to discuss alternative treatment options.

6.7.1.2. Analgesic Therapy

If a participant experiences significant pain after baseline, one of the following analgesic regimens may be initiated at any time:

- Ibuprofen (at a dose of up to 800 mg orally every 6 hours) not to exceed 3200 mg/24 hours.
- Acetaminophen not to exceed 4 g/24 hours.

If pain is not sufficiently controlled with one of the above regimens, a revised analgesic regimen can be considered in consultation with the sponsor or designee.

Dose modifications in these analgesics on an as needed basis up to the maximum permitted dose and frequency are allowed during the study.

Analgesic usage (yes/no) will be recorded daily (see Study Manual).

6.7.1.3. Antiseptic Therapy

Permitted antiseptic washes are limited to one of the following: chlorhexidine gluconate, triclosan, benzoyl peroxide, or diluted bleach in bathwater.

6.7.1.4. Wound Care

Concomitant use of wound care dressings on HS wounds is allowed. Options are limited to alginates, hydrocolloids, and hydrogels.

6.7.2. Prohibited Medications and Procedures

The following medications are prohibited for all participants **in the study**:

- JAK inhibitors, systemic or topical (eg, ruxolitinib, tofacitinib, baricitinib, filgotinib, lesataurtinib, and pacritinib).
- Adalimumab or any other TNF- α treatment or any investigational or experimental treatments.
- Systemic immunosuppressive or immunomodulating drugs (eg, oral or injectable corticosteroids, methotrexate, cyclosporine, and azathioprine) except as described in Sections 6.7.3 and 8.2.4.
- Systemic therapies for HS (eg, retinoids and antiandrogens) with potential therapeutic impact for HS.
- Surgical, laser, or IPL intervention in area with HS lesion, except as specified in Section 8.2.4 for rescue lesional treatment.
- Systemic anti-infectives (eg, antibiotics, antivirals, and antifungals), except as described in Section 6.7.1.1 for antibiotic therapy, or topical anti-infectives on HS lesions.
- Conventional therapies with potential therapeutic impact for HS.
- Topical antiseptic washes, creams, soaps, ointments, gels, and liquids containing antibacterial agents to treat HS, except those listed in Sections 6.7.1.3 and 6.7.1.4.
- Potent systemic CYP3A4 inhibitors or inducers (see Study Manual) or fluconazole.
Note: Topical agents with limited systemic availability are permitted.
- Concomitant uses of P-gp inhibitors and inducers (refer to the Study Manual) need to be consulted with the medical monitor.
- Live vaccines (during the study and within 6 weeks after EOT).

